# Sample size

We initially estimated the sample size needed based on the precision around efficacy estimates for lefamulin in a single arm study and estimated that a total of 30 patients with complete data on tests of cure, adherence, and adverse events would provide precision to estimate efficacy  $\geq$ 90% with binomial exact 95% Cl's ranging from 73.5% - 99.9%. Assuming loss to follow-up of up to 30%, **a total of 40 patients will need to be enrolled**.

Because there are fewer people in each arm of a two-arm randomized pilot trial, the statistical power and precision will be somewhat than that estimated for a single arm study. Table 2 compares precision for an arm with 20 randomized persons to one with 30 randomized persons. Even in the case where an arm has only 20 randomized persons, the lower bound of the confidence intervals is >60%, which would still demonstrate benefit.

**Table 2**: Precision around estimated cure rates assuming 40 patients are enrolled and outcome data are available on either 20 participants randomized per arm (if neither regimen meets criteria for futility), or 30 participants randomized to an arm (if one of the regimens meets criteria for futility)

Lefamulin	N=20		N=30	
failures (n)	Estimated cure	95% confidence	Estimated cure	95% confidence
		intervals		intervals
3	85%	62.11 – 96.79	90%	73.5 – 97.9
2	90%	68.30 - 98.77	93%	77.9 – 99.2
1	95%	75.13 – 99.87	96%	82.8 - 99.9

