# **Criteria for futility**

Given the absence of alternative therapies for *M. genitalium* treatment failures, even modest efficacy of 60% would be useful for some patients. Therefore, futility will be defined as <5% probability that true efficacy is 60% (or higher), given the number of treatment failures that occur in the first 10 patients. The probability of observing three or fewer cures (e.g., at least 7 treatment failures) in the first 10 patients if the true efficacy is 60% is 5%. Therefore, if three or fewer of the first ten patients in either arm experience microbiologic cure, we would declare futility for that regimen.

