# Data analysis

We will calculate and present simple proportions and 95% CIs for each of our outcomes. We will not require complete data on all outcomes to be included in analyses. Instead, the denominator will be the total number of patients for whom we have complete outcome data for the outcome of interest. For example, patients with test of cure data but without clinical cure data will be included in the calculation of microbiologic cure but excluded from the calculation of clinical cure.

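### The sample-size figures do not fit together: 30 complete patients at 30% loss needs 43 enrolled, not 40, and the lower bound above 60% in an arm of 20 holds only with few failures and little loss

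*Combined protocol and SAP*

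**What the plan says.** The Sample size section starts from a single-arm calculation. The investigators "estimated that a total of 30 patients with complete data on tests of cure, adherence, and adverse events" would give adequate precision for an efficacy of 90% or more. They then write "Assuming loss to follow-up of up to 30" per cent, and conclude that "a total of 40 patients will need to be enrolled".

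The section next turns to the two-arm design. Table 2 gives exact 95% intervals for 1, 2 and 3 failures with N=20 and N=30. Its caption describes this as precision "assuming 40 patients are enrolled and outcome data are available on either 20 participants randomized per arm", or on 30 if one regimen is dropped. The text draws the conclusion: "Even in the case where an arm has only 20 randomized persons, the lower bound of the confidence intervals is >60" per cent, and it takes this as enough to show benefit.

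Two other sections bear on the point. Criteria for futility explains the benchmark: "even modest efficacy of 60% would be useful for some patients". Data analysis states "We will not require complete data on all outcomes to be included in analyses", and that "the denominator will be the total number of patients for whom we have complete outcome data for the outcome of interest".

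**The concern.** There are two separate problems. First, 30 complete, 30% loss and 40 enrolled cannot all be right together.

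Second, the sentence about the lower bound carries no condition, although it depends on two. It covers only the failure counts tabulated, and Table 2 stops at the last count for which the statement is true. It also needs outcome data on essentially everyone randomised. The 40 enrolled were justified as 30 plus an allowance for loss, yet Table 2 treats all 40 as evaluable, so the same 10 patients serve both as cover for loss and as data.

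The sample size rests on precision alone, and this sentence is the stated reason that 20 per arm is adequate after the move from one arm to two. A reader who accepts it would think an interval clear of the 60% benchmark is secured, when it depends on the results and on retention.

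**Working it through.** **Inputs.** 30 complete patients, loss up to 30%, 40 enrolled, 20 or 30 per arm, exact binomial 95% intervals (Sample size and Table 2); benchmark 60% (Criteria for futility); denominator limited to patients with the outcome (Data analysis).

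**1. Reproduce Table 2.** For x cures among n, the two-sided Clopper-Pearson limits are: lower = 2.5% quantile of Beta(x, n−x+1); upper = 97.5% quantile of Beta(x+1, n−x).

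| Failures | n=20 | n=30 |
|---|---|---|
| 3 | 62.11 to 96.79 | 73.47 to 97.89 |
| 2 | 68.30 to 98.77 | 77.93 to 99.18 |
| 1 | 75.13 to 99.87 | 82.78 to 99.92 |

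All six intervals agree with the plan.

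**2. Enrolment.** Required N = complete / (1 − loss).
- At 30% loss: 30/0.70 = 42.9, so 43. The stated 40 is not reproduced.
- 40 × 0.70 = 28 complete.
- 40 × 0.75 = 30, so 40 matches 25% loss. Another possible source is 30 × 1.3 = 39, rounded up, which is not a valid inflation for loss.
- Effect on precision at 3 failures: lower bound 71.8% (25/28) against 73.5% (27/30).

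**3. The lower bound with full data, n=20.** 3 failures gives 62.1%; 4 failures (80% cure) gives 56.3%; 5 failures (75% cure) gives 50.9%. The statement stops being true at the first row not shown.

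**4. The lower bound with loss from an arm of 20.** The plan's 30% gives 20 × 0.70 = 14 evaluable; 25% gives 20 × 0.75 = 15.

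| Evaluable | Most failures with bound above 60% | Bound there | Bound with one more failure |
|---|---|---|---|
| 20 | 3 | 62.1% | 56.3% |
| 19 | 3 | 60.4% | 54.4% |
| 18 | 2 | 65.3% | 58.6% |
| 16 | 2 | 61.7% | 54.4% |
| 15 | 1 | 68.1% | 59.5% |
| 14 | 1 | 66.1% | 57.2% |

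So with 3 failures the statement survives the loss of one patient but not two. With 2 failures it survives the loss of four but not five. With 1 failure it still holds at 14 evaluable.

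**5. The retained arm of 30.** 30 × 0.70 = 21 evaluable: 3 failures gives 63.7%, 4 failures gives 58.1%. At about 90% cure, 19/21 gives 69.6% against 73.5% for 27/30. With all 30 evaluable, up to 6 failures keeps the bound above 60% (61.4%).

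**6. How likely is a bound above 60%?** It needs 17 or more cures of 20, or 13 or more of 14. The binomial probabilities are:

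| True cure | 20 evaluable | 14 evaluable |
|---|---|---|
| 80% | 0.411 | 0.198 |
| 85% | 0.648 | 0.357 |
| 90% | 0.867 | 0.585 |

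**The case against.** The best defence is that the sentence summarises Table 2 and should be read with it. The caption states the assumption of available outcome data, the rows show 1 to 3 failures, and the statement is true of every N=20 row. The plan works from an efficacy of 90% or more, so the 85% row is already below plan and 80% lies outside it. The 30% is a ceiling, tied to complete data on several outcomes, so loss on the primary outcome may well be lower. The enrolment gap hardly moves the interval. No decision uses the lower bound: futility is judged on cure counts, and the final intervals will use the actual denominators.

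Much of this stands. The conditions are missing from the sentence, not from the section; 14 and 21 evaluable are worst cases; and no decision rule changes. But the caption's assumption of full data conflicts with the loss allowed just above it. Nor is 4 failures in an arm remote, since Study Design itself reports several early failures after lefamulin alone.

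A further objection is that holding failures fixed while n falls also lowers the cure rate: 3 failures of 18 is 83.3% cure, not 85%. That is fair for this example, but not for the others. Two failures of 15 is 86.7% cure and 2 of 14 is 85.7%. Both are above the 85% for which Table 2 gives 62.1%, yet their bounds are 59.5% and 57.2%. There the fall is lost precision.

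**Conclusion.** The concern holds. Enrolment of 40 does not follow from the plan's own inputs: it is 3 short of 43 and yields 28 complete patients at the stated loss. The effect on single-arm precision is small, under 2 percentage points on the lower bound at 3 failures.

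The statement about an arm of 20 matters more. It fails with full data at 4 failures (56.3%), and at 3 failures once two patients have no test-of-cure result (58.6%). At 25% loss, the only rate at which 40 enrolled yields 30 complete, 2 failures already fails (59.5%).

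The 14-evaluable figures assume that the whole 30% falls on the primary outcome and equally in both arms. The result at 4 failures of 20 needs no assumption about loss. The Table 2 intervals, the futility rule and the planned analysis are not in question.

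**What to change.** Revise the text and the table; enrolment can stay at 40.

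1. Say either that 40 enrolled gives 28 complete patients at 30% loss, or that 30 complete assumes 25% loss.
2. Extend Table 2 with columns for 14 and 21 evaluable, labelled as the worst-case loss allowed, beside the no-loss 20 and 30. A 4-failure row would show where the bound falls below 60%:

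| Failures | n=14 | n=20 | n=21 | n=30 |
|---|---|---|---|---|
| 4 | 41.9 to 91.6 | 56.3 to 94.3 | 58.1 to 94.6 | 69.3 to 96.2 |
| 3 | 49.2 to 95.3 | 62.1 to 96.8 | 63.7 to 97.0 | 73.5 to 97.9 |
| 2 | 57.2 to 98.2 | 68.3 to 98.8 | 69.6 to 98.8 | 77.9 to 99.2 |
| 1 | 66.1 to 99.8 | 75.1 to 99.9 | 76.2 to 99.9 | 82.8 to 99.9 |

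3. Replace the unconditional sentence with its condition: the lower bound exceeds 60% with at most 3 failures among 20 evaluable patients, 1 among 14, or 3 among 21.

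The cost is a few sentences and two table columns, with no change to enrolment, analysis or decision rules. The stated precision becomes less favourable.

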# Data analysis

We will calculate and present simple proportions and 95% CIs for each of our outcomes. We will not require complete data on all outcomes to be included in analyses. Instead, the denominator will be the total number of patients for whom we have complete outcome data for the outcome of interest. For example, patients with test of cure data but without clinical cure data will be included in the calculation of microbiologic cure but excluded from the calculation of clinical cure.

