# Study Design

We propose to provide compassionate access to lefamulin and estimate the efficacy of lefamulin in treating antibiotic resistant MG through a coordinating center at the University of Washington (UW). We will enroll a total of 40 symptomatic patients with MG infections who have experienced treatment failure after moxifloxacin and/or other second or third line antimicrobials

or in whom moxifloxacin is contraindicated. Patients will be followed for 42 or 56 days, depending on the regimen they receive.

There is an increasing global trend to pre-treat MG infections with doxycycline to reduce organism load. There have also been several initial reports of treatment failure after a 7-day regimen of lefamulin alone, but successes after a regimen in which patients were pre-treated with doxycycline in the companion study in Melbourne, Australia. Therefore, we propose to also determine if pre-treatment with doxycycline is necessary. To simultaneously assess the efficacy of lefamulin alone (600mg orally twice daily for 7 days), and a regimen incorporating pre-treatment with doxycycline 100mg orally twice daily for 7 days followed by lefamulin 600mg orally twice daily for 7 days), we will randomize the first 20 patients to either Regimen A (lefamulin alone) or Regimen B (pretreatment with doxycycline followed by lefamulin) in a 1:1 ratio.

An interim analysis will be performed after the first 20 patients are enrolled to assess the efficacy of each of these two regimens for futility. Based on the results of this interim analysis, we will make one of three possible decisions:

- If neither of the regimens meet criteria for futility, we will continue randomizing patients to one of the two regimens until we have reached our target sample size of 40 patients (20 randomized per arm).
- If one of the regimens meets criteria for futility but the other regimen does not, we will drop the regimen that met futility criteria and continue to administer the other regimen to the remaining 20 patients for a total of 30 randomized patients in the retained regimen.
- If both regimens meet criteria for futility, we will halt the study and reassess the possibility of using alternative dosing regimens.

Criteria for futility are outlined in the section on sample size on p. 6.

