## **Outcomes**

We will assess one primary outcome and five secondary outcomes.

- Primary Outcome
  - Microbiologic cure defined as a negative Aptima MG test 21-28 days after completing lefamulin
- Secondary Outcomes
  - Microbiologic cure, as defined above, after lefamulin alone compared to microbiologic cure after sequential treatment with doxycycline followed by lefamulin
  - Clinical cure defined as absence of symptoms, absence of visible discharge, and absence of other clinical signs (<5PMNs/hpf on Gram stained smear where available) 21-28 days after completion of the lefamulin
  - Reported adherence to lefamulin (defined by self-reported number of tablets taken)
  - Reported adverse events (defined by self-reported adverse events)
  - Sustained microbiologic cure defined as a negative Aptima MG test 42-47 days after completing lefamulin

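### The regimen comparison is a listed secondary outcome, but the plan names no between-arm estimate for it and promises a firmer conclusion than 40 patients can give

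*Combined protocol and SAP*

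**What the plan says.** The Study Design section gives the reason for randomizing: "we propose to also determine if pre-treatment with doxycycline is necessary". The first 20 patients are allocated 1:1 to Regimen A (lefamulin alone) or Regimen B (doxycycline, then lefamulin). If neither regimen is futile, randomization continues "until we have reached our target sample size of 40 patients (20 randomized per arm"). If one is dropped, the remaining 20 patients all receive the other, "for a total of 30 randomized patients in the retained regimen".

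The first secondary outcome is "Microbiologic cure, as defined above, after lefamulin alone compared to microbiologic cure after sequential treatment with doxycycline followed by lefamulin".

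The Data analysis section has one method: "We will calculate and present simple proportions and 95% CIs for each of our outcomes". The rest of that section is a denominator rule, under which each outcome is analysed in the patients who have data for it.

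The Criteria for futility section judges each arm against a fixed 60% cure rate. The Sample size section works from single-arm precision, and Table 2 gives intervals for a single arm of 20 or 30.

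**The concern.** A comparison is not a simple proportion, so the stated method does not by itself produce the stated outcome. No section says which contrast will be estimated, how its interval will be formed, or which patients enter it if a regimen is dropped.

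Two misreadings become possible. Overlapping arm-level intervals could be taken as no difference when the difference is distinguishable from zero. Two similar arms could be taken as showing that pre-treatment is unnecessary when a gap of around 20 points is still compatible with the data. Either would affect the question that randomization was added to address. Leaving the contrast open also allows the method to be chosen after the results are seen.

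**Working it through.** **Inputs from the documents.** 20 per arm if both regimens continue; 30 and 10 if one is dropped (Study Design). Loss to follow-up of up to 30% and exact binomial 95% intervals (Sample size). Denominator restricted to patients with outcome data (Data analysis). With 30% loss, 20 × (1 − 0.30) = 14 evaluable per arm. The cure counts used below for the comparison are illustrative.

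**1. Reproduce Table 2.** The Clopper-Pearson limits for x cures of n are the 0.025 quantile of Beta(x, n − x + 1) and the 0.975 quantile of Beta(x + 1, n − x). For n = 20 with 3, 2 and 1 failures: 62.11-96.79, 68.30-98.77 and 75.13-99.87. For n = 30: 73.5-97.9, 77.9-99.2 and 82.8-99.9. All six match. Each describes one arm.

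**2. Overlapping intervals with a clear difference.** Take 17/20 (B) against 10/20 (A).
- The exact intervals are 62.1-96.8 and 27.2-72.8, which overlap between 62.1 and 72.8.
- The Newcombe interval uses each arm's Wilson limits (l, u): lower = d − √[(p₁ − l₁)² + (u₂ − p₂)²]; upper = d + √[(u₁ − p₁)² + (p₂ − l₂)²].
- The Wilson limits are 0.6396-0.9476 and 0.2993-0.7007, and d = 0.85 − 0.50 = 0.35.
- Lower: 0.35 − √(0.2104² + 0.2007²) = 0.35 − 0.291 = 0.059.
- Upper: 0.35 + √(0.0976² + 0.2007²) = 0.35 + 0.223 = 0.573.
- The difference is 35 points, 95% CI 5.9 to 57.3; Fisher p = 0.041.

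This is not an isolated case. At 20 per arm there are 21 × 20 / 2 = 210 unequal result pairs, ignoring which arm is higher. In 47 of them the exact intervals overlap while the Newcombe interval excludes zero, and in 35 of those 47 Fisher p is also below 0.05. This counts possible results and says nothing about how likely they are.

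**3. Equal arms that settle little.** When both arms have the same result, the half-width is √[(p − l)² + (u − p)²]. For 18/20 the Wilson limits are 0.6990-0.9721, so the half-width is √(0.2010² + 0.0721²) = 0.214.

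| Cures in each arm | 95% CI for the difference (points) |
|---|---|
| 20/20 | ±16.1 |
| 19/20 | ±19.1 |
| 18/20 | ±21.4 |
| 14/20 | ±26.8 |
| 13/14 (after 30% loss) | ±25.0 |

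**4. One regimen dropped.** Only the first 20 patients, 10 against 10 before losses, are then a randomized comparison; the other 20 all receive the retained regimen. Meeting the futility rule in one arm is not a between-arm result. For 7/10 against 3/10 the Wilson limits are 0.3968-0.8922 and 0.1078-0.6032. The difference is 0.40, with lower limit 0.40 − √(0.3032² + 0.3032²) = −0.029 and upper limit 0.40 + √(0.1922² + 0.1922²) = 0.672. The interval of −2.9 to 67.2 points includes zero.

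**5. Power, on assumed cure rates.** The documents give no pair of rates for the comparison. With a two-sided 5% Fisher test, 60% against 90% has power 0.49 at 20 per arm and 0.32 at 14. For 70% against 90% it is 0.24 and 0.14.

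**The case against.** The only stated objective is to estimate the efficacy of lefamulin. The Sample size section calls the study a pilot and accepts that two arms give different power and precision from one. The comparison is one of five secondary outcomes, and the futility decision needs only arm-level estimates. Intervals are promised for every outcome, and the first secondary outcome is itself a comparison, so the Data analysis sentence can be read as covering it. A reader could in any case derive a difference from two reported proportions and their denominators.

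Much of this stands. A reader might infer that the plan cannot answer its question at all. That goes too far: very different arms would be informative, and the difference is recoverable from the reported counts. A reader might also infer that the arms will be compared by whether their intervals overlap. The plan says no such thing; the overlap example shows what arm-level intervals can hide. Low power for a secondary outcome of a pilot is not a defect in itself.

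What does not fall away is that no contrast, interval method or comparison population is named for an outcome the plan lists, and that the wording of the aim is stronger than estimation.

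**Conclusion.** The point holds as a gap between the comparative aim and the stated analysis. The plan gives arm-level proportions only, and it says it will settle whether pre-treatment is needed with a sample that leaves the difference uncertain by roughly 20 points or more either way in most of the equal-arm cases shown. It is worth correcting because the remedy is simple, but it touches a secondary outcome and leaves the primary outcome and the futility rule intact.

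The widths rest on the Newcombe method and on illustrative counts. A reader might take ±21 to ±25 points as the best attainable. It is not: 19/20 in each arm gives ±19.1 and 20/20 gives ±16.1, while 14/20 gives ±26.8. The power figures rest on assumed cure rates and support a more modest aim; they do not show that the trial is too small for its stated objective.

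**What to change.** - **Data analysis:** state that the first secondary outcome will be analysed as the risk difference in 21-28-day microbiologic cure, Regimen B minus Regimen A, with a Newcombe or Miettinen-Nurminen 95% CI (choose one in advance). Use concurrently randomized patients only: both full arms if neither is dropped, and the first 20 (10 against 10 before losses) if one is. Do not pool the later non-randomized patients into a 30-against-10 contrast.
- **Study Design:** replace the promise to determine necessity with an aim to estimate the difference in cure between regimens.
- **Beside Table 2:** add precision for the difference, labelled as illustrative: about ±21 points if 18/20 are cured in each arm and ±25 if 13/14 are (after 30% loss), narrower near complete cure (±19 at 19/20 each) and wider at lower rates (±27 at 14/20 each).
- **Power:** if any figure is quoted, label its cure rates as assumptions.

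The cost is a few sentences and one extra line of analysis, with no added patients or visits. The downside is a more modest stated aim.

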# Inclusion Criteria:

- Physician referral
- Persistent symptomatic urogenital MG infection documented by any NAAT 14-90 days after completion of the prior antimicrobial regimen for MG
- Low risk of reinfection defined as no unprotected sex with an untreated sex partner since completion of the prior antimicrobial regimen
- Male or female sex at birth
- ≥18 years of age
- English-speaking
- Able to provide written informed consent
- Able to undergo a test to confirm MG infection at baseline and tests of cure 21-28 days and 42-47 days after completing lefamulin

- Referring physician willing and able to provide needed patient information
- Living in the US

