## Exclusion Criteria:

- Females with PID, pregnancy, or currently breastfeeding
- Females of reproductive age not on a highly effective method of contraception (i.e., IUD, Nexplanon, progesterone only depot injection with last injection <3 months, or oral contraceptive pill and last menstrual period <28 days prior)
- Known QT prolongation, ventricular arrhythmias including torsades de pointes
- Receiving concurrent drugs known to prolong QT interval (e.g., Class IA or Class III antiarrhythmics, antipsychotics, erythromycin, pimozide, moxifloxacin, tricyclic antidepressants).
- Receiving strong or moderate CYP3A or P-gp inducers, strong CYP3A or P-gp inhibitors, moderate CYP3A or P-gp inhibitors or sensitive CYP3A4 substrates that prolong QT interval
- Moderate or severe liver impairment
- Renal failure requiring dialysis
- Known allergy to doxycycline, other tetracyclines, and/or lefamulin
- Known liver disease
- Not willing or unable to undergo a test to confirm MG infection at baseline and tests of cure 21-28 days and 42-47 days after completion of lefamulin
- Not fluent in English and/or not able to provide written informed consent
- Referring physician unwilling or unable to provide needed patient information
- At the study physician's discretion
- Rectal MG infection only

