#### Dispensing lefamulin (and doxycycline, as warranted)

[name] will be the prescribing physician of record and partner with the UW Harborview Medical Center Investigational Drug Services (HMC IDS) to check for drug interactions and/or contraindications to lefamulin (and doxycycline for patients randomized to sequential therapy). Lefamulin and doxycycline will be stored in and dispensed from the UW HMC IDS Pharmacy, which will serve as the pharmacy of record. This is a locked, temperature-controlled facility adjacent to the PHSKC Sexual Health Clinic that manages and dispenses all medications for research studies conducted at the Harborview campus. HMC IDS will be responsible for tracking, documentation, and return/disposal of any unused drug provided by Nabriva.

Upon receipt of a prescription from [name], HMC IDS will prepare the medication packet(s). The research coordinator will ship the medication packet(s) to the patient. Mailing antibiotics across state lines is permissible with an IND exemption in place, which is the case here. Per our consultation with a clinical trials pharmacist, "when a clinical study is found to be IND exempt [21 CFR 312.2(b)], the FDA has granted that study the same permissions as a study with an IND (such as placing investigational drug into interstate commerce). ... with a documented IND exemption, ... the drug can be shipped across state lines when a subject has been enrolled in the study [21 CFR 312.40]." (full text of letter noting on file in the regulatory binder). The FDA has granted this study an IND exemption, cross-referencing Nabriva Therapeutics' existing IND. In addition to the lefamulin tablets, the medication package will include a drug information sheet for lefamulin; contact information for any patient questions about the antibiotic, side effects, or both; a letter, which provides an overview of the study; a specimen collection instruction sheet for each specimen; a return shipment instruction sheet; and materials for patients to collect and return two specimens (one specimen for culture and assessment of MICs; the other specimen to confirm MG infection at baseline). For patients randomized to sequential therapy, the medication package will also contain doxycycline tablets and a drug information sheet for doxycycline.

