#### **Culture Specimens**

Each medication package will include one Copan flocked swab, one vial of Copan Universal Transport Medium [UTM]), and materials and instructions for returning culture specimens to the UW Global Health STI Laboratory. Male patients will be instructed to collect a self-obtained meatal swab and place it into the tube containing UTM before the first dose of lefamulin (or doxycycline if randomized to sequential therapy) is taken. Female patients will be instructed to take a self-obtained vaginal swab as described above. Both types of self-obtained swabs have demonstrated comparable sensitivity and specificity for diagnostic testing relative to clinician obtained swabs, and are acceptable to patients. Additional culture specimen collection materials and instructions will be included along with the Aptima test kits mailed out for tests of cure (see below).

Upon receipt in the Global Health STI Laboratory at the UW, culture specimens will be stored immediately at -70°C or colder. They will subsequently be shipped in batches to [name] laboratory at Statens Serum Institute. [name] laboratory is one of only a few worldwide with the demonstrated capacity to consistently cultivate *M. genitalium* and perform antimicrobial resistance testing. His laboratory will perform the culture and susceptibility testing for lefamulin, as well as for azithromycin and moxifloxacin, under a separate contract. Performing culture and MICs will enable us to assess whether there is any pre-existing resistance to lefamulin, whether any resistance to lefamulin is selected for during treatment, and whether the efficacy of lefamulin differs for azithromycin-resistant and moxifloxacin-resistant strains.

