## Tests of cure

Tests of cure will be performed in the UW Global Health STI Laboratory (laboratory director [name]). The Hologic Aptima MG assay, which we propose to use for tests of cure, has higher sensitivity and specificity than most other assays. Thus, test-of-cure windows when using this assay are generally longer (21-28 days) than when other assays are used. Furthermore, instances of MG recrudescing after an initial negative test subsequent to treatment have been reported, suggesting that additional follow-up after an initial test of cure is warranted in studies of novel antimicrobials. Therefore, we will perform two tests of cure (one at 21-28 days and one at 42-47 days after completion of lefamulin).

The research coordinator will ship Aptima test kits to enrolled patients, one 21-48 days, and one 42-47 days after completion of Lefamulin. In addition to the Aptima collection kit and instructions and shipping materials to return the Aptima tubes to the UW Global Health STI Laboratory, that package will also include materials and instructions for culture specimen collection as described above. Culture specimens will be shipped at the same time as the test of cure specimens.

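### A patient negative on the baseline confirmation specimen and negative at 21-28 days counts as a cure; the efficacy population should be defined by the baseline result

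*Combined protocol and SAP*

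**What the plan says.** - **Outcome.** The Outcomes section gives the primary outcome as "Microbiologic cure defined as a negative Aptima MG test" 21-28 days after completing lefamulin. It sets no condition on baseline status. Sustained cure at 42-47 days is defined in the same way.
- **Denominator.** Under Data analysis, "the denominator will be the total number of patients for whom we have complete outcome data for the outcome of interest". Anyone with a test-of-cure result enters the microbiologic cure calculation.
- **Entry.** The Inclusion Criteria require "Persistent symptomatic urogenital MG infection documented by any NAAT 14-90 days after completion of the prior antimicrobial regimen for MG", together with low reinfection risk. For the study's own baseline test they ask only that the patient can undergo it, and the matching exclusion is "Not willing or unable to undergo a test to confirm MG infection at baseline". A positive result is not required.
- **Baseline specimen.** Under Enrollment and consent, eligibility is confirmed before prescribing. Under Dispensing, the medication package carries materials for two specimens, one for culture and "the other specimen to confirm MG infection at baseline".
- **Timing and assay.** The Culture Specimens section says the culture swab is taken "before the first dose of lefamulin (or doxycycline if randomized to sequential therapy) is taken". No equivalent statement appears for the confirmation specimen. The assay is named only for follow-up: "The Hologic Aptima MG assay, which we propose to use for tests of cure".
- **Interim.** Under Study Design, "An interim analysis will be performed after the first 20 patients are enrolled". Under Criteria for futility, a regimen is dropped if three or fewer of its first ten patients are cured.

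**The concern.** The objective is efficacy against *M. genitalium* infection. The plan collects a specimen that can show whether infection was still present when treatment began, but then makes no use of the result. The result cannot act as an entry gate, because the kit travels with the drug. Since it has no role in the analysis either, a patient whose infection had already cleared is scored as a lefamulin success.

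The error has one direction: such patients add to the numerator and the denominator together. Two results are exposed. One is the primary cure proportion in each arm. The other is the futility decision, which becomes less likely to drop a weak regimen. A weak arm is a real possibility, since the Study Design section itself reports early failures of lefamulin alone. If the rule is settled only after outcomes are known, the choice is post hoc, in arms of 20 where one patient is worth 5 percentage points (1/20).

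**Working it through.** **Inputs from the plan.** Futility rule: 3 or fewer cures in ten, with reference efficacy 60% and a stated probability of 5% (Criteria for futility). Arm sizes of 20 or 30, and loss to follow-up of up to 30% (Sample size).

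**Assumed input.** b is the share of patients negative at baseline, who are taken to be negative again at 21-28 days. The documents give no value; 5, 10 and 20% are shown. p is the true cure rate in infected patients.

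**Step 1: reproduce the plan's figure.** For X ~ Bin(10, 0.6), P(X ≤ 3) = 0.0001 + 0.0016 + 0.0106 + 0.0425 = 0.0548. The plan's 5% is this figure rounded. The exact intervals in Table 2 also reproduce, for example 17/20: 62.1 to 96.8%.

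**Step 2: apparent cure rate.** Apparent cure = b + (1 − b)p.

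| True cure p | b = 5% | b = 10% | b = 20% |
|---|---|---|---|
| 60% | 62% | 64% | 68% |
| 90% | 90.5% | 91% | 92% |

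For example, 0.10 + 0.90 × 0.60 = 0.64.

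**Step 3: effect on the futility rule.** The chance of stopping is P(Bin(10, b + (1 − b)p) ≤ 3), with test-of-cure results for all ten patients.

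| True cure p | b = 0 | b = 5% | b = 10% | b = 20% |
|---|---|---|---|---|
| 30% | 65.0% | 55.5% | 46.0% | 28.8% |
| 40% | 38.2% | 31.0% | 24.5% | 14.1% |
| 60% | 5.5% | 4.1% | 3.1% | 1.6% |

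**Step 4: what the interim repair must preserve.** Removing baseline-negative patients but keeping 3 or fewer on the smaller number would change the error rate. At a true 60%, P(X ≤ 3) is 9.9% with nine patients and 17.4% with eight. Applying the rule to ten evaluable patients from the baseline-defined population keeps it at 5.5%. It also returns the chance of stopping a true 30% regimen to 65%, if all ten are infected.

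**Step 5: effect on the interval.** With 3 failures in an arm of 20, the exact lower bound is 62.1%. If one of the 17 cures was baseline-negative and is removed, 16/19 gives 60.4%; if two, 15/18 gives 58.6%. Part of this fall is only the smaller n: losing patients for any reason does the same (12/14 gives 57.2%).

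**The case against.** The strongest reply is that this is silence rather than intent. The Study Design section enrols patients with *M. genitalium* infections, the specimen is described as confirmatory, and the denominator sentence is about missing data across outcomes, its example being test-of-cure data without clinical-cure data. That is fair as to intent, and a reader should not infer that the investigators chose to count uninfected patients. But the two sections taken together do count them, and nothing elsewhere takes them out.

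The second reply is about size, and it largely stands. Patients must have symptoms, a positive referral NAAT and low reinfection risk, so b is probably small. At 5% the estimate moves by 2 points or less, against Table 2 intervals more than 20 points wide for an arm of 20 with two or three failures. Two stronger readings are tempting. One is that the primary estimate is substantially inflated or the futility look defeated. That needs b near 20%, and no figure in the documents supports it. The other is that the plan's claim of a lower bound above 60% fails for this reason. Step 5 shows that ordinary loss to follow-up produces a similar fall. Nor does the plan predict 90% cure; it uses that figure as a precision scenario.

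On timing, baseline ordinarily means before treatment, and the package includes a collection instruction sheet that is not shown. This is a point to state explicitly, not evidence of error.

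A reader might also infer that the interim needs a set of lower cut-offs for fewer than ten evaluable patients. The documents do not support that. Suppose 30% of results are missing, a missing result is read as not a cure, and b is 5%. The present rule then stops a true 30% regimen about 81% of the time (per-patient cure chance 0.70 × 0.335 = 0.2345). Cut-offs reset to keep the 60%/5% criterion at each smaller number would stop it only about 38% of the time.

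**Conclusion.** The gap is in the text and does not depend on any assumption: as written, a patient negative at baseline and at 21-28 days is a cure in the primary estimate and among the ten patients per arm behind the futility decision. The bias is upward for any patient who is truly uninfected.

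Its size rests wholly on an assumed b. It is modest near 90% true cure (at most 2 points for b up to 20%), larger at the plan's 60% benchmark (2 to 8 points), and most visible at the interim for a weak regimen (65% down to 55, 46 or 29% at a true 30%, given ten results per arm). Because the entry criteria probably keep b low, the lower end of these ranges is the more plausible. The repair is cheap and uses a specimen already planned, so the change should be made. The point does not show that the trial's conclusions would be wrong.

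**What to change.** 1. Define the primary microbiologic-cure population as patients with test-of-cure data who are not negative on the baseline confirmation specimen. State that this specimen is collected before the first dose of any study drug (before doxycycline in Regimen B), and name the assay.
2. Keep patients with a missing or invalid baseline result, on the basis of their qualifying NAAT.
3. Use the same population for sustained cure at 42-47 days.
4. Report cure in all tested patients as a sensitivity analysis. Keep all patients for adherence and side effects.
5. At the interim, apply the existing rule (3 or fewer cures in ten; 5.5% exact at a true 60%) to the first ten patients per arm in this population who have a test-of-cure result. Do not add cut-offs for smaller numbers.

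**Cost.** No new specimen is needed. Slightly fewer patients are evaluable, so intervals widen. Infected patients with a false-negative baseline leave the primary estimate but remain in the sensitivity analysis. The bias is reduced, not removed, because patients with a missing baseline stay in.

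The interim look comes later. The number enrolled per arm to reach ten evaluable is about 10 / [(1 − loss)(1 − b)]. With no loss and b = 5%, that is 10/0.95 = 10.5, or about 11 per arm. With the plan's 30% loss it is 10/(0.70 × 0.95) = 15.0. Much of that delay comes from loss to follow-up and not from the baseline rule. If enrolment continues meanwhile, the Study Design figure of 30 in a retained arm needs restating: 15 per arm at the look leaves 40 − 30 = 10 patients, so 15 + 10 = 25.
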